8. EFFICACY ANALYSIS

Not applicable.

9. SAFETY ANALYSIS

All randomized subjects who received at least one dose of IMP will be included in the safety analysis. All results will be summarized using the FAS by actual treatment group and CVL-871 Combined, which is defined as combined CVL-871 treatment groups.

The observation periods include:

- The pre-treatment period is defined as the time up to first administration of the IMP.
- The on-treatment period is defined as the time from the first administration of the IMP (on Day 1) to the last administration of the IMP + 28 days.
- The post-treatment period is defined as the time from the last administration of the IMP + 29 days to the end of the study follow-up.

9.1. Adverse Events

The adverse event (AE) types include:

- **Pre-treatment adverse events** are adverse events that developed up to the first administration of the IMP.
- **Treatment-emergent adverse events (TEAEs)** are adverse events that developed or worsened or became serious during the treatment period.
- **Post-treatment adverse events** are adverse events that developed or worsened or became serious after the treatment period.

The primary focus of adverse event reporting will be on TEAEs. Pre-treatment and post-treatment adverse events will be summarized separately.

All AEs will be coded to a PT and associated primary SOC using the version of MedDRA in effect at the time of database lock.

Adverse events will be recorded from the time of signed informed consent until the end of the study or the resolution/stabilization of all SAE and adverse event of special interest (AESI).

If an adverse event date/time of onset (occurrence, worsening, or becoming serious) is incomplete, an imputation algorithm will be used to classify the adverse event as pre-treatment, treatment-emergent, or post-treatment. The algorithm for imputing date/time of onset will be conservative and will classify an adverse event as treatment-emergent unless there is definitive information to determine it is pre-treatment or post-treatment. Details on classification of adverse events with missing or partial onset dates are provided in [Section 17.2](#).

Adverse events will be summarized by primary SOC and PT, sorted by the internationally agreed SOC order ([MedDRA® Data Retrieval and Presentation: Points to Consider, 2022](#)) and decreasing frequency of PTs in high dose group within SOC unless otherwise specified. In case of equal frequency regarding PTs, alphabetical order will be used. Multiple occurrences of the same event in the same patient will be counted only once in the tables within a treatment phase. The denominator for computation of percentages will be the FAS within each treatment group.

On top of the analysis planned below, all TEAEs, all treatment emergent SAEs, TEAEs leading to permanent treatment discontinuation and TEAEs leading to death will be summarized by treatment group.

Overview summaries of the number and percentages of patients within the following categories will be provided by treatment group and overall for:

- Any TEAE
- Any study drug related TEAE
- Any TEAE of Common Terminology Criteria for Adverse Events (CTCAE) Grade 3 or higher
- Any Serious TEAE
- Any Serious TEAE considered study drug related
- Any TEAE leading to permanent treatment discontinuation
- Any TEAE of special interest
- Any Serious TEAE of special interest
- Any AE leading to death

The overview summaries for pre-treatment AEs, TEAEs and post-treatment AEs will be provided based on the FAS.

Individual listings (AEs, SAEs, AEs leading to permanent treatment discontinuation, AEs leading to death, AESI) will be provided to support the summary tables based on the FAS.

9.1.1. Incidence of Adverse Events

The following TEAE summaries will be generated for the FAS, for each treatment group and overall.

- All TEAEs presented by PT, showing number and percentage of patients with at least 1 TEAE, sorted by decreasing incidence of PT in the high dose treatment group
- All pre-treatment AE presented by primary SOC and PT, showing number and percentage of patients with at least 1 AE
- All TEAEs presented by primary SOC and PT, showing number and percentage of patients with at least 1 TEAE
- All post-treatment AE presented by primary SOC and PT, showing number and percentage of patients with at least 1 AE
- Common TEAEs (PTs with an incidence $\geq 5\%$ in any treatment group) by primary SOC and PT
- Common TEAEs (PTs with an incidence $\geq 2\%$ in either CVL-871 treatment group and greater than placebo group) by primary PT

- Relationship of adverse events to study drug

The following TEAE summaries will be generated for the FAS, for each treatment group and overall:

- All TEAEs by relationship, presented by primary SOC and PT, showing the number and percentage of patients with at least 1 TEAE

9.1.2. CTC Grade of Adverse Events

The following TEAE summaries will be generated for the FAS, for each treatment group and overall.

- All TEAEs by maximal reported CTCAE grade, presented by primary SOC and PT, showing the number and percentage of patients with at least 1 TEAE by maximal CTCAE grade.

9.1.3. Serious Adverse Events

The following TEAE summaries will be generated for the FAS, for each treatment group and overall.

- All serious TEAEs, presented by primary SOC and PT, showing the number and percentage of patients with at least 1 serious TEAE
- All serious TEAEs by relationship, presented by primary SOC and PT, showing the number and percentage of patients with at least 1 serious TEAE

9.1.4. Adverse Events Leading to Permanent Treatment Discontinuation

The following TEAE summaries will be generated for the FAS, for each treatment group and overall.

- All TEAEs leading to permanent treatment discontinuation, presented by primary SOC and PT, showing the number and percentage of patients with at least 1 TEAE leading to permanent treatment discontinuation

9.1.5. Adverse Events Leading to Study Discontinuation

The following TEAE summaries will be generated for the FAS, for each treatment group and overall.

- All TEAEs leading to study discontinuation, presented by primary SOC, and PT, showing the number and percentage of patients with at least 1 TEAE leading to study discontinuation

9.1.6. Adverse Events of Special Interest (AESI) as Defined in Protocol

As defined in CSP Section 8.4.6, Adverse Events of Special Interest (AESI) include:

- Symptoms suggestive of symptomatic orthostatic hypotension:
 - Syncope

- Presyncope requiring stabilization to avoid fall
- Generalized weakness, sensations described as dizziness or lightheadedness, visual blurring or darkening of the visual fields, and, in severe cases, loss of consciousness
- Grade 3 nausea, defined as inadequate oral caloric or fluid intake; tube feeding, total parenteral nutrition, or hospitalization indicated
- Grade 2 vomiting, defined as vomiting requiring outpatient intravenous hydration or other medical intervention (eg, anti-emetic)
- Abnormal liver function tests:
 - Treatment-emergent value of $>3 \times$ the upper limit of normal (ULN) for ALT or AST and $>2 \times$ ULN for total bilirubin
 - Treatment-emergent value of $>3 \times$ ULN for ALT or AST and clinical jaundice
- Abnormal dreams/nightmares
- Adverse events potentially related to abuse (as provided in the Abuse Potential Monitoring Plan [APMP])
- Adverse events leading to discontinuation of IMP or from the trial

The following AESI summaries will be generated for the FAS, for each treatment group and overall.

- All TEAEs of special interest, presented by primary SOC and PT, showing the number and percentage of patients with at least 1 TEAE of special interest
- All serious TEAEs of special interest, presented by primary SOC and PT, showing the number and percentage of patients with at least 1 serious TEAE of special interest

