8.4.6.1 Symptoms Suggestive of Symptomatic Orthostatic Hypotension

- Syncope
- Presyncope requiring stabilization to avoid fall
- Generalized weakness, sensations described as dizziness or lightheadedness, visual blurring or darkening of the visual fields, and, in severe cases, loss of consciousness

8.4.6.2 *Nausea Grade 3*

- Grade 3 nausea, defined as inadequate oral caloric or fluid intake; tube feeding, total parenteral nutrition, or hospitalization indicated

8.4.6.3 *Vomiting Grade 2 or Higher*

- Grade 2 vomiting, defined as vomiting requiring outpatient intravenous hydration or other medical intervention (eg, anti-emetic)

8.4.6.4 *Abnormal Liver Function Tests*

The finding of an elevated value for alanine aminotransferase (ALT) or aspartate aminotransferase (AST) of $>3 \times$ the upper limit of normal (ULN) in combination with either an elevated value for total bilirubin $>2 \times$ ULN or clinical jaundice in the absence of cholestasis or other causes of hyperbilirubinemia is considered to be an indicator of severe liver injury. Investigators must report the occurrence of either of the following as AESI to the sponsor with 24 hours:

- Treatment-emergent value of $>3 \times$ ULN for ALT or AST and $>2 \times$ ULN for total bilirubin
- Treatment-emergent value of $>3 \times$ ULN for ALT or AST and clinical jaundice

8.4.6.5 *Abnormal Dreams/Nightmares*

Either of the following AEs:

- Abnormal dreams
- Nightmares

8.4.6.6 *Adverse Events Potentially Related to Abuse*

A key objective of the Abuse Potential Monitoring Plan (APMP) is to monitor for instances of abuse or diversion of the trial medication and other psychoactive substances.

In addition to monitoring for irregularities in medication handling, AEs that may be suggestive of a developing abuse issue will also receive special attention. As part of the APMP, medication handling irregularities (MHIs) must be reported, and AEs related to abuse potential and AEs involving MHIs must be reported as events subject to additional monitoring (ESAMs), with detailed narratives.

Investigators and site staff at each trial site will be trained on reporting potentially abuse-related AEs (eg, recording a description of the event in the subject's own words in the source documents as well as the eCRF, in addition to the clinical term, and to be aware that a subject's report may encompass more than one event and that these should

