
Assessment of Intensity	

All AEs, including clinically significant treatment-emergent laboratory abnormalities, will be graded according to the National Cancer Institute–Common Terminology Criteria for Adverse Events, version 5.0 (NCI-CTCAE v5.0; https://ctep.cancer.gov/protocoldevelopment/electronic_applications/docs/CTCAE_v5_Quick_Reference_5x7.pdf)
 
Adverse events not listed by the NCI-CTCAE will be graded according to the criteria defined below.
	
Grade	Description
1	Mild; asymptomatic or mild symptoms; clinical or diagnostic observations only; intervention not indicated.
2	Moderate; minimal, local or noninvasive intervention indicated; limiting age-appropriate instrumental activities of daily living.
3	Severe or medically significant but not immediately life-threatening; hospitalization or prolongation of hospitalization indicated; disabling; limiting self-care ADL.
4	Life-threatening consequences; urgent intervention indicated.
5	Fatal AE; an event that results in the death of the subject.

Note: An instrumental activity of daily living refers to preparing meals, shopping for groceries or clothes, using the telephone, managing money, etc.
	
Assessment of Causality	

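### The SAP's AESI list gives vomiting as Grade 2 only, where the protocol category is Grade 2 or higher; a flag programmed literally from the SAP would drop Grade 3+ vomiting that meets no other AESI criterion

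*SAP*

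**What the plan says.** Protocol Section 8.4.6.3 is headed "Vomiting Grade 2 or Higher". One bullet follows. It describes Grade 2 vomiting and does not mention higher grades.

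SAP Section 9.1.6 carries in its title that the AESIs are those the protocol defines, and it opens with "As defined in CSP Section 8.4.6, Adverse Events of Special Interest (AESI) include". Its vomiting entry is "Grade 2 vomiting, defined as vomiting requiring outpatient intravenous hydration or other medical intervention (eg, anti-emetic", which is the protocol bullet without the heading above it. No other SAP text extends the vomiting category above Grade 2.

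The same SAP list has a separate entry, "Adverse events leading to discontinuation of IMP or from the trial", which applies at any grade and corresponds to protocol Section 8.4.6.7.

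SAP Section 9.1.6 builds two tables on the list: TEAEs of special interest and serious TEAEs of special interest, each by system organ class and preferred term. The overview in SAP Section 9.1 adds the row "Any TEAE of special interest" and a matching row for serious events.

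**The concern.** Safety and tolerability are the primary objective. Both documents say the slow titration is there to mitigate nausea and vomiting (protocol Section 4.3, SAP Section 3.4), so vomiting is one of the events a reader will look for among the AESIs.

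A severity threshold that loses its upper part behaves oddly: moderate vomiting is flagged and severe vomiting is not. The grades at risk are also those more likely to be serious. The protocol's general scale, used for events that CTCAE does not list, describes Grade 3 as "Severe or medically significant but not immediately life-threatening; hospitalization or prolongation of hospitalization indicated; disabling; limiting self-care ADL", and inpatient hospitalization is a seriousness criterion in protocol Table 11. The documents do not reproduce CTCAE's own definitions of vomiting above Grade 2, so this is an indication only.

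There is a consistency risk too. Under protocol Section 8.4.6, sites report AESIs on SAE timelines, and each subject with an AESI gets a brief narrative. Sites that follow the protocol heading will report Grade 3 vomiting as an AESI. A table programmed from the SAP bullet would omit it, so narratives and tables could disagree.

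**Working it through.** No stated figure is in question, so the check is a comparison of texts.

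**1. Is the SAP meant to differ from the protocol?** No. Section 9.1.6 names protocol Section 8.4.6 as its source. SAP Section 15 lists four departures: the added 95% confidence intervals, the Screened label, the mITT definition and the missing-value strategy. None concerns AESIs.

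**2. Is the upward extension in the protocol heading only loose wording?** Probably not. The preceding subsection, 8.4.6.2 on nausea, names Grade 3 with no such extension. The two adjacent headings are worded differently, and the SAP entry for vomiting loses that difference.

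**3. What does each rule select?**

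| Vomiting TEAE | Protocol heading | SAP list, read literally |
|---|---|---|
| Grade 2 | AESI | AESI |
| Grade 3 or above, leading to discontinuation of IMP or from the trial | AESI | AESI, through the discontinuation entry |
| Grade 3 or above, meeting no other AESI entry | AESI | not selected |

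Only the last row differs.

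**4. Can the last row occur?** Yes. Protocol Section 4.1.2 requires discontinuation for intolerance at Step 2, at Step 3 on rechallenge and at Step 4. On first exposure to Step 3, and at Step 5, it lets a subject who cannot tolerate the dose return to the previous step and stay in the trial. Severe vomiting at either point need not lead to discontinuation.

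**5. Which outputs are exposed?** The two AESI tables in SAP Section 9.1.6, the two AESI rows of the overview in Section 9.1, and the supporting AESI listing if it uses the same flag.

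**6. Which outputs are not exposed?**
- The overview row for any TEAE of CTCAE Grade 3 or higher (SAP Section 9.1).
- All TEAEs by system organ class and preferred term (Section 9.1.1).
- "All TEAEs by maximal reported CTCAE grade, presented by primary SOC and PT" (Section 9.1.2).
- The serious TEAE tables, if the event is serious (Section 9.1.3).

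**7. How are patients counted?** The AESI tables count patients with at least one event. A patient who also has a separately recorded Grade 2 vomiting TEAE stays in the vomiting row of the all-AESI table. A patient with any other AESI stays in the overall count. The all-AESI table therefore loses a patient from the vomiting row only if all of that patient's vomiting of Grade 2 or above falls in the last row of the table in step 3.

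**8. How many patients is that?** The documents give no event counts, so this cannot be computed.

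**The case against.** The strongest reply is that the SAP defers to the protocol. Section 9.1.6 names protocol Section 8.4.6 as its source, so a programmer who goes back to it will see the heading and include the higher grades. The SAP also does not say that the flag is derived from CTCAE grade. Protocol Sections 8.4.6 and 10.3.4 have sites enter AESIs in the electronic data collection tool, and tables built on those reports would keep Grade 3 and above. This stands, and it makes the loss conditional on programming from the SAP bullet. It does not make the bullet right: the SAP is the document that gives the detailed methodology, and it should not depend on the reader noticing a heading elsewhere.

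A second reply is that the slip starts in the protocol, whose heading and bullet do not match. That is correct, and it means the protocol needs attention as well as the SAP.

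Three stronger readings are tempting, and the documents do not support them:
- A reader might infer that all Grade 3 or higher vomiting disappears from the AESI outputs. It does not, because the discontinuation entry catches part of it.
- A reader might infer that the trial's severe vomiting, or the primary endpoint of TEAE incidence and severity, would be under-reported. It would not, because the outputs in step 6 of the working report these events in full.
- A reader might put a size on the loss by taking one missed subject in a planned arm of 25, 1/25 = 4 percentage points. That divides a hypothetical case by an arm size the trial did not reach. SAP Sections 3.1 and 15 state that enrollment closed early and the planned sample size was not achieved.

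**Conclusion.** The mismatch is real. SAP Section 9.1.6 presents as the protocol's definition a vomiting category narrower than the protocol's heading, and no departure is declared. Taken literally, the SAP list leaves Grade 3 or higher vomiting that meets no other AESI entry out of the two AESI tables and the AESI overview rows.

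This consequence rests on two conditions: that the flag is programmed from the SAP bullet and not from the protocol heading or the sites' AESI reports, and that at least one such event occurs. The number affected cannot be stated from the documents. The defect is confined to the AESI outputs. It is still worth correcting before those tables are programmed, because safety is the primary objective, vomiting is an expected tolerability problem, and the correction is exact and cheap.

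**What to change.** 1. Reword the vomiting entry in SAP Section 9.1.6 to carry the full protocol category, "Vomiting Grade 2 or Higher", with the Grade 2 description kept as the threshold.
2. Derive any grade-based AESI flag for vomiting as CTCAE grade ≥ 2. State in the SAP whether the AESI tables use a derived flag, the sites' AESI reports, or both.
3. Reconcile the heading and bullet of protocol Section 8.4.6.3 so that the two documents cannot be read differently. If a protocol change is not practical, record the reading used in SAP Section 15.

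The cost is a few words in the SAP, one programming condition and a short clarification. No new data are needed. The change aligns the analysis definition with the category the protocol heading already states.

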4.1.2 Treatment Period

The dose of CVL-871 will be titrated in a blinded fashion to either 1.0 mg QD or 3.0 mg QD and then maintained for the duration of the 12-week Treatment Period, as shown in Table 3. Subjects will be administered a combination of CVL-871/placebo tablets across all doses throughout the trial to maintain the trial blind.

Table 3 CVL-871 and Placebo Dosing Schedule

Trial Day	Titration Step	Target Dose		Placebo QD
		CVL-871 1.0 mg QD	CVL-871 3.0 mg QD	
Days 1-3:	Step 1	0.25 mg CVL-871 QD	0.25 mg CVL-871 QD	Placebo QD
Days 4-7:	Step 2	0.5 mg CVL-871 QD	0.5 mg CVL-871 QD	Placebo QD
Days 8-16:	Step 3	1.0 mg CVL-871 QD	1.0 mg CVL-871 QD	Placebo QD
Days 17-21:	Step 4	1.0 mg CVL-871 QD	2.0 mg CVL-871 QD	Placebo QD
Days 22-84:	Step 5	1.0 mg CVL-871 QD	3.0 mg CVL-871 QD	Placebo QD

Abbreviation: QD = once daily.

This titration scheme will be implemented for all treatment groups, including placebo, in a blinded fashion for all subjects who are randomized. Exceptions for subjects who experience tolerability issue at specific time points are described below.

The first dose of investigational medicinal product (IMP; Step 1) will be taken at the trial site at the Baseline Visit (Day 1). No deviations in the titration schedule up through Step 2 are allowed. Subjects who cannot achieve or tolerate the dose at Step 2 must be discontinued from the trial.

On Day 8 (Visit 3), subjects will take the Step 3 dose of IMP at the clinic. Subjects will be monitored for tolerability while undergoing concurrent assessments; after completion of all visit procedures, the investigator will assess whether the participant will continue with the new dose. Subjects who are unable to tolerate the dose at Step 3 may go back to the dose at Step 2. These subjects will remain at the Step 2 dose until Day 13, at which time they will again receive the Step 3 dose (rechallenge). Subjects will be instructed to call the site on Day 14 (day after they again receive the Step 3 dose) to ensure that they can tolerate the rechallenge. Subjects who are unable to tolerate the Step 3 dose upon rechallenge will be discontinued from the trial.

On Day 17, all subjects will take the Step 4 dose; subjects will be contacted by phone on Day 18 and evaluated for tolerability after the dose increase. Subjects who are unable to tolerate the Step 4 dose will be discontinued from the trial.

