8.4.6.7 Adverse Events Leading to Discontinuation

Any AE that leads to discontinuation of IMP or from the trial will be classified as an AESI.

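### SAP 9.1.6 pools all AESIs by SOC and PT, discontinuation events included, so no planned table counts each subject once per AESI category

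*SAP*

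**What the plan says.** Protocol 8.4.6 has seven AESI subsections. Six name a specific concern: orthostatic symptoms, nausea, vomiting, liver tests, abnormal dreams, and events potentially related to abuse. Some are narrow. The nausea criterion in 8.4.6.2 is "Grade 3 nausea, defined as inadequate oral caloric or fluid intake" and does not cover lower grades. The orthostatic category is broad, covering syncope, presyncope needing stabilization, and "Generalized weakness, sensations described as dizziness or lightheadedness, visual blurring or darkening of the visual fields".

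The seventh, 8.4.6.7, depends on neither term nor grade: "Any AE that leads to discontinuation of IMP or from the trial will be classified as an AESI". SAP 9.1.6 carries it over as "Adverse events leading to discontinuation of IMP or from the trial".

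SAP 9.1.6 then plans two AESI tables: "All TEAEs of special interest, presented by primary SOC and PT" and "All serious TEAEs of special interest, presented by primary SOC and PT". Neither is broken down by AESI category or grade. The overview in SAP 9.1 has one row for any special-interest TEAE and one for serious ones, also pooled.

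Protocol 4.1.2 gives CTCAE Grade 2/3 as its example of intolerance. It requires discontinuation for intolerance at Step 2, at the Step 3 rechallenge and at Step 4: "Subjects who are unable to tolerate the Step 4 dose will be discontinued from the trial".

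The heading of protocol 8.4.6.3 covers vomiting of Grade 2 and above, while SAP 9.1.6 lists Grade 2 vomiting only.

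**The concern.** Safety and tolerability is the primary objective. A reader opens an AESI table to learn how many subjects in each arm met each prespecified concern. A layout by SOC and PT does not answer that where a category spans several terms, where it rests on a combination of laboratory values, or where one term holds events that qualified for different reasons.

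The discontinuation category adds to this. A Grade 2 nausea that ends titration becomes an AESI and falls in the same row as Grade 3 nausea. The mixing need not be equal across arms: in protocol Table 3 the Step 4 dose rises from 1.0 to 2.0 mg in the 3.0 mg arm and stays at 1.0 mg in the 1.0 mg arm. More Step 4 drop-outs in one arm would raise its special-interest nausea count even if severe nausea were the same in both.

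**Working it through.** The plan states no figure on this point, so there is nothing to reproduce. The check follows each protocol category through the planned layout and then asks whether another SAP output supplies the count.

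| Protocol category | Where it falls in the AESI table | Subject count elsewhere in the SAP |
|---|---|---|
| 8.4.6.1 Orthostatic symptoms | Several PTs and SOCs | None for the symptom category; SAP 9.3 covers standing blood pressure |
| 8.4.6.2 Nausea | Nausea row, with lower-grade nausea that led to stopping | Yes, SAP 9.1.2 (maximal grade by PT) |
| 8.4.6.3 Vomiting | Vomiting row, with any lower-grade event that led to stopping | SAP 9.1.2, once the grade range is settled |
| 8.4.6.4 Liver | Whatever PT is reported | None; SAP 9.2.2 summarizes each parameter separately, and the criterion is joint |
| 8.4.6.5 Dreams | One row per PT | No category total |
| 8.4.6.6 Abuse-related | Scattered over PTs | None; the protocol describes a sponsor term search, but the SAP plans no table for it |
| 8.4.6.7 Discontinuation | Any PT | Yes, SAP 9.1.4, 9.1.5 and 13.1 |

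**Orthostatic total.** If a subjects appear in one PT row and b in another, the category count lies anywhere from max(a, b) to a + b. Illustration with 25 per arm and a = b = 2: each row shows 2/25 = 8%. If the same two subjects had both symptoms, the category rate is 2/25 = 8%. If they are four different subjects, it is 4/25 = 16%. The rows look identical in both cases.

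**Overview row.** Let A be the subjects with any of the six specific concerns and D those with an AE that led to stopping. The row reports the size of A or D combined. The size of A alone is then known only to lie between (A or D) − D and (A or D), an interval as wide as D. Subtracting the discontinuation count does not recover A, because a subject who stopped for syncope belongs to both.

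**Size of D.** The planning discontinuation rate is 20% from all causes (protocol 9.2, SAP 4.1). The documents do not give the share due to AEs, so I assume 25% to 100%.

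- 25 per arm: 0.20 × 25 = 5 discontinuations; 0.25 × 5 = 1.25 to 1.00 × 5 = 5 subjects.
- 20 per arm: 0.20 × 20 = 4 discontinuations; 0.25 × 4 = 1 to 1.00 × 4 = 4 subjects.
- As a proportion: 0.20 × 0.25 = 5% to 0.20 × 1.00 = 20% of an arm.

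**Nausea row.** Illustrative counts with 25 per arm: three Grade 2 nausea drop-outs and one Grade 3 nausea give an AESI nausea row of 4/25 = 16%. Those meeting 8.4.6.2 itself number 1/25 = 4%. Both are correct answers to different questions, and the AESI table shows only the first.

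**The case against.** The strongest reply is that most of this information is reported elsewhere. SAP 9.1.2 tabulates every TEAE by maximal CTCAE grade and PT, so Grade 3 nausea can be compared between arms. SAP 9.1.4, 9.1.5 and 13.1 separate the events that led to stopping, the last by titration and later period. SAP 9.1 plans AESI and discontinuation listings, and protocol 8.4.6 requires a brief narrative for each subject with an AESI. The trial is exploratory, its safety analysis is descriptive, and no decision rule in these documents uses the AESI row. Enrollment closed below the planned size, so reading listings by hand is feasible. All of this stands, and it limits the point to reporting.

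A reader might infer three stronger things that the documents do not support.

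- *That orthostatic events cannot be told apart from titration drop-outs, or that no orthostatic rate exists.* The AESI table has PT rows. Syncope and dizziness qualify in their own right, so stopping because of them adds no foreign events to those rows. SAP 9.3 also summarizes standing changes of at least 20 mmHg systolic and 10 mmHg diastolic. Only the once-per-subject symptom total is missing.
- *That the nausea row overstates the AESI rate fourfold.* Under protocol 8.4.6.7, 4/25 is the correct number of subjects with an AESI of that term. The 16% against 4% contrast uses invented counts and shows mixing, not error.
- *That every intolerance becomes an AESI through stopping.* First intolerance at Step 3 and intolerance at Step 5 allow a return to the previous dose under protocol 4.1.2.

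The table shells are in a separate document and may hold more detail than the SAP text.

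**Conclusion.** The point holds as a reporting weakness in the summary of the primary objective. As written, the SAP gives no once-per-subject count by AESI category. For the orthostatic symptom category, the joint liver criterion and abuse-related events, no other planned table supplies it. The any-AESI overview row also takes in every treatment-emergent AE that led to stopping: about 1 to 5 subjects per arm at 20 to 25 per arm, if the planning discontinuation rate applies and 25% to 100% of it is due to AEs. Some of those subjects would also meet a specific criterion. Arms may be smaller than this, since enrollment closed early and the documents do not give the number randomized.

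No data are lost and no estimate is biased. The change is worth making because it is cheap and answers the question that the AESI list was written to ask.

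**What to change.** In SAP 9.1.6, summarize AESIs by protocol categories 8.4.6.1 to 8.4.6.7, counting each subject once per category, with PT nested within category. Show separately the AESIs that qualify only through discontinuation. In the SAP 9.1 overview, keep the present row and add one for any AESI excluding those that qualify only through discontinuation.

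Reconcile the vomiting definition between the protocol 8.4.6.3 heading and SAP 9.1.6 before programming, because a category table needs a single definition.

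The cost is SAP wording, one more table shell and some event-level review. Most categories follow from PT, grade, laboratory values and action taken. Presyncope needing stabilization may have to be assigned from AESI reports or narratives, and abuse-related events from the term search that the protocol already plans. No new subject data are needed.
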